1.1 Title

Comparing the effects of three different support surfaces on the skin function of heel and sacral skin after loading

1.2 Protocol version

Version 1, September 25, 2015

1.3 Funding

This investigator initiated study (IIS) is conducted by the Clinical Research Center for Hair and Skin Science, Department of Dermatology and Allergy, Charité – Universitätsmedizin Berlin. The trial is supported by Stryker®. Stryker® provides the three support surfaces (IsoAir, IsoGel and basic foam mattress).

2.1 Background and Rationale

Pressure ulcers (PUs) are localized injuries of the skin and/or underlying soft tissues due to prolonged deformation (NPUAP, EPUAP, PPPIA 2014). In adults in supine position the lateral areas of the heel and the sacral area are most often affected (PU predilection sites). PUs are severe injuries and wounds causing a substantial burden on patients, caregivers, and on healthcare systems worldwide. There is common agreement, that effective PU prevention is of crucial importance to maintain skin and tissue integrity in individuals at risk. Besides risk assessment and repositioning the use of special PU preventive support surfaces are the key interventions in PU prevention. Support surfaces may be broadly classified into active (e.g. alternating mattresses) and reactive (e.g. special foams). These support surfaces allow a more even “pressure distribution” leading to lesser deformation of the skin and soft tissues and/or to alternating loading and off-loading to limit the time of localized compression.

In recent years the concept of “microclimate” received increasing attention. It is defined as the temperature, humidity, and air-flow on and near to the skin surface. The parameters of skin temperature and humidity are closely related to functional and mechanical skin properties and to the susceptibility to PU development (Gefen 2011, NPUAP, EPUAP, PPPIA 2014). Therefore, many support surfaces try to influence the microclimate as well. A major methodological challenge in current PU research is the lack of outcomes to measure the effects of preventive approaches. PU incidence is clearly the clinical most relevant parameter. However, using this dichotomous outcome well conducted RCTs require hundreds of patients, long recruitment and follow-up periods, and are expensive. In addition, there is a debate whether the current definition of PU incidence in clinical trials is really the best choice (Kottner, Gefen 2012). Widely agreed upon Core Outcomes Sets (Clarke, Williamson 2015) have not been developed in PU research so far (Nixon 2015). Attempts have been made, to identify possible other parameters serving as predictors or biomarkers for PU risk and/or early tissue damage, e.g. skin temperature, shear wave velocity based on ultrasound elastography, epidermal cytokines, or serum myoglobin. It is well known, that skin function for instance in terms of transepidermal water loss (TEWL) is very sensitive marker of skin barrier changes. TEWL increases are usually associated with skin barrier impairments whereas TEWL decreases are associated with an intact or improved skin barrier (Rogiers et al. 2001). Using a standard hospital mattress, it was shown recently that this parameter shows a loading time depend increases in the lateral heel areas indicating subclinical skin damage (Kottner et al. 2015). Skin temperature and erythema increased as well; both being directly related to the risk of tissue damage. These functional parameters were also partly

related to changes in skin surface topography and elasticity (Dobos et al. 2015). Taken together, these results indicate that the prolonged loading causes changes in skin structure and function. PU preventive support surface modify the degree of skin and tissue deformation and/or skin temperature and moisture. Therefore, an association between the type and working mechanism of a PU support surface and skin function after loading is highly likely. Furthermore, such a relationship may be used to characterize and/or to quantify the performance PU support surfaces in terms of skin protection.

2.2 Objectives

The overall aim of this explorative study is to measure skin responses of the two most common PU predilection sites (heel, sacral skin) after two hours loading on three different support surfaces and the sternal skin (control area). The following objectives are determined:

- (1) To measure the changes of skin temperature, erythema, stratum corneum hydration, TEWL, skin roughness and elasticity before loading (baseline) and after two hours loading at the right heel and sacral on three different support surfaces and the sternal skin area.
- (2) To quantify possible differences in skin response between the support surfaces.

2.3 Trial design

This exploratory study is a randomized and controlled trial, with a cross-over design (every subject will lie on every support surface).

3 Methods: Participants, interventions, and outcomes

3.1 Eligibility criteria

Inclusion criteria

- Healthy, female volunteers
- 60 to 80 years
- Body Mass Index between 18.5 and 29.9 kg/m²
- Non-Smoker of at least one year
- Absence of skin diseases or scars in the skin areas of interest
- Ability to move independently and to maintain supine and prone positions
- Able to give written informed consent
- No use of cosmetic products or topical applied drugs on the study areas at least 12 hours before measurement
- Skin phototype I to III according to Fitzpatrick classification
- Willing and able to fulfil the study requirements

These criteria are chosen because they reflect the target group and results will be comparable with the previous study (Kottner et al. 2015, Dobos et al. 2015). This would enhance interpretation.

Exclusion criteria

- Disability to maintain in supine or prone position
- Acute diseases
- Acute or chronic diseases with increased or decreased body temperature ($\leq 35^{\circ}\text{C}$ or $\geq 38,5^{\circ}\text{C}$, measured in the ear)
- History or establishment of Diabetes or pre-diabetes, cardiac or renal insufficiency, atopic dermatitis, psoriasis, chronic obstructive pulmonary disease (COPD)
- Acute or chronic wounds in the skin areas of interest
- Any skin affection which may interfere with the study assessment, e.g. tattoo, psoriasis or scar on the investigational sites
- Participation in another clinical study 4 weeks before inclusion visit
- Current participation in any other clinical study

3.2 Interventions

After giving informed consent and checking the in- and exclusion criteria, the subjects will be randomized into three study groups (three different support surfaces):

- (1) Alternating Low Pressure mattress with low air loss function (IsoAir, stryker, USA)
- (2) Reactive support surface, gel mattress (IsoGel, stryker, USA)
- (3) Standard mattress (basic foam)

The support surfaces will be used according to the manufacturer instructions. Every subject will lie on every mattress. Therefore, every subject will have at least three visits in the study center of approximately 4 hours. The order of mattress use will be randomized for the visits.

The study volunteers will be requested, to acclimatize for 30 min at 40-60% relative humidity and a temperature of 20-22°C with having the right lateral heel, sacral and sternal skin uncovered. During this time the right lateral heel skin, the sacral and sternal skin will be marked in prone position. Once in prone position the baseline skin measurements on the right lateral heel and sacral skin will be conducted (order see below: Sequence of measurements), that no/minimal interferences between measurements occur (Kottner et al. 2014). After that, the participants will stay in supine position for two hours. The baseline sternal skin measurements will be performed immediately after the subjects turned into supine position. At the end of two hours the sternal skin measurements will be repeated. After two hours, the subjects turn into prone position again and the skin measurements on the right lateral heel and sacral skin will be conducted again to capture the effect of the two hour loading on the mattress. The measurements will be repeated after 20 min to observe the adjustments after offloading. Study procedures and measurements will be conducted always and only in the morning to minimize possible circadian influences. The procedures will be performed on all visits in the same way and order, only the support surface will change.

Sequence of measurements:

- (1) TEWL
- (2) Skin surface temperature
- (3) Stratum corneum hydration (SCH)
- (4) Erythema
- (5) Epidermal and dermal hydration
- (6) Skin elasticity
- (7) Skin roughness
- (8) Taking of OCT images (only for standard mattress (basic foam))

Measurements will be performed two times per measurement area. Every value will be recorded separately.

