3.3 Outcomes and variables

Because this is an exploratory study, no distinction will be made between primary and secondary outcomes.

Table 1. Outcomes

Name	Method and metric	Time points of data collection
TEWL	
 · Tewameter TM 300 (Courage + Khazaka, Cologne, Germany) · Means of duplicate measurements per skin area in g/m²/h 	BL, after 2 hours and 20 minutes after loading
Erythema	
 · Mexameter MX 18 · Means of duplicate measurements per skin area in arbitrary units 	BL, after 2 hours and 20 minutes after loading
SCH	
 · Corneometer CM 825 (Courage + Khazaka, Cologne, Germany) · Means of duplicate measurements per skin area in arbitrary units 	BL, after 2 hours and 20 minutes after loading
Skin roughness	
 · Visioscan VC 98 · Images of skin structure · Rz and Ra in µm 	BL, after 2 hours and 20 minutes after loading
Skin elasticity/deformability	
 · Cutometer MPA 580 (Courage& Khazaka, Germany) · Means of duplicate measurements per skin area in mm 	BL, after 2 hours and 20 minutes after loading
Skin surface temperature	
 · Measurement with Skin-Thermometer ST 500 · (Courage+Khazaka electronic GmbH) · Means of duplicate measurements per skin area in °C per skin area 	BL, after 2 hours and 20 minutes after loading
Epidermal and dermal hydration	
 · Measurement with MoistureMeterEpiD (Delfin Technologies) · Percentage of tissue water (0-100%) (0,5mm measurement depth) 	BL, after 2 hours and 20 minutes after loading
Epidermal/dermal characteristics (only for basic foam)	
 · OCT (Thorlabs, Lübeck, Germany), image processing and measurements according Trojahn et al. 2015 · Descriptive 	BL and after 2 hours
Skin thickness (only for basic foam)	
 · OCT (Thorlabs, Lübeck, Germany), image processing and measurements according Trojahn et al. 2015 · µm (metric) 	BL and after 2 hours

Table 2. Variables

Name	Method and metric	Time points
Age	Checking by looking at the ID card (metric)	Inclusion
Body temperature	Clinical thermometer in °C	BL, after two hours
Heart rate	Beats per minute (bpm)	BL, after two hours
Blood pressure	Millimeters of mercury (mmHg)	BL, after two hours
BMI (body height, weight)	kg/m ²	Inclusion
Phototype	Categories I, II, III	Inclusion

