3.4 Participant timeline

Table 3. Participant timeline

	Inclusion	V1, V2, V3*				
		0 to 30 min (acclimatization)	Baseline measurements	2 hours (supine position)	Prone position	Prone position after 20 minutes
In-/exclusion criteria	x					
Signed Informed consent	x					
Demographics	x					
BMI	x					
Physical examination	x					
Marking of measurement areas	x					
Randomization	x					
Heart rate	x					
Blood pressure	x					
Body temperature	x					
Skin measurements at sternal skin			x	x		
Skin measurements at right heel and sacral skin			x		x	x
Adverse events monitoring		x	x	x	x	x

*same protocol on V1, V2, V3 (only change of support surface depending on randomized order), V3: end of study

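### OCT on foam visits only contradicts the identical-visits rule and leaves the 20-minute recovery comparison open to a timing difference that cannot be separated from foam

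*Combined protocol and SAP*

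**What the plan says.** All references are to the combined protocol and SAP.

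- **The rule.** Section 3.2: "The procedures will be performed on all visits in the same way and order, only the support surface will change". The footnote to Table 3 (section 3.4) says the same: "same protocol on V1, V2, V3 (only change of support surface depending on randomized order".
- **The exception.** The list below the rule in section 3.2 gives step 8 as "Taking of OCT images (only for standard mattress (basic foam". Table 1 (section 3.3) restricts both OCT outcomes in the same way: "Epidermal/dermal characteristics (only for basic foam" and "Skin thickness (only for basic foam". Their time points are "BL and after 2 hours".
- **The other measurements.** Table 1 schedules the seven remaining outcomes at "BL, after 2 hours and 20 minutes after loading".
- **The recovery round.** Section 3.2: "The measurements will be repeated after 20 min to observe the adjustments after offloading".

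Neither the rule nor the footnote mentions the OCT exception. The plan gives no OCT duration and no matching step for the other two visits, and section 5.2 does not mention the difference.

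**The concern.** The second objective (section 2.2) is to quantify differences in skin response between surfaces. A cross-over serves that aim well when the surface is the only thing that changes within a subject. Here a second thing changes with it: the foam visit alone includes two OCT sessions. One closes the baseline round before loading; the other closes the post-load round before the recovery round. Any effect of the added time or procedure would be read as an effect of foam, and foam enters two of the three pairwise comparisons.

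The plan itself treats interference between measurements as a matter to control, since it fixes their order for that reason. It also leaves the start of the 20-minute interval loose in section 3.2, and the consequence of the foam-only step depends on that start.

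**Working it through.** The plan gives no figure on this point, and the sample-size statement in section 3.5 does not enter. The check compares the passages, tests for aliasing and looks at the two possible clocks.

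**1. Where OCT falls on a foam visit (sections 3.2 and 3.3)**

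| Stage | IsoAir, IsoGel | Foam |
|---|---|---|
| Prone baseline, heel and sacrum | steps 1–7 | steps 1–7, then OCT |
| Turn supine, sternal baseline | follows step 7 | follows OCT |
| Two hours supine, sternal repeat | same | same |
| Prone post-load round | steps 1–7 | steps 1–7, then OCT |
| 20-minute round | steps 1–7 | steps 1–7 |

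OCT is last in its round, so it cannot affect readings in that round. The two-hour heel and sacral readings can be reached only through the baseline OCT, which adds prone time before loading. The sternal baseline is taken later on foam. The 20-minute round is the only heel and sacral round that follows a post-load OCT.

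**2. Aliasing.** Table 4 has 6 orders x 3 periods = 18 cells. Foam fills 6 of them, one per order; OCT occurs in those 6 and in none of the other 12. The correlation of the OCT and foam indicators is 1.0. A model with sequence (6 columns), period (2) and surface (2) has rank 10; adding an OCT indicator leaves it at 10. The IsoAir–IsoGel contrast is untouched, since neither visit has OCT.

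**3. The two clocks.** Let R be the length of the seven-step post-load round and D the length of OCT, both in minutes and neither given.

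- *Clock from the end of the post-load round.* The recovery round starts R + 20 minutes after off-loading on IsoAir and IsoGel, and R + D + 20 on foam. Foam is read D minutes later.
- *Clock from off-loading.* The recovery round starts at 20 minutes on every visit, but R + D must fit into 20 minutes on foam where only R must fit elsewhere. With 7 steps x 2 sites x 2 readings = 28 readings (section 3.2 asks for two per area), the time available per reading is 1200 s / 28 = 43 s without OCT. With D assumed to be 5 or 10 minutes it is 900 / 28 = 32 s or 600 / 28 = 21 s.

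**4. Scale under the end-of-round clock (assumptions only).** Assume exponential decay with a half-life h of 10 to 30 minutes and D of 5 to 10 minutes. The relative loss in the response still present is 1 − 2^(−D/h). As a share of the initial response the loss is at most 2^(−20/h) − 2^(−(20+D)/h), which takes R = 0; a longer R makes it smaller.

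| h | D | Relative loss | Share of initial response, at most |
|---|---|---|---|
| 10 | 5 | 29% | 0.250 − 0.177 = 7% |
| 10 | 10 | 50% | 0.250 − 0.125 = 12.5% |
| 30 | 5 | 11% | 0.630 − 0.561 = 7% |
| 30 | 10 | 21% | 0.630 − 0.500 = 13% |

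Under an off-loading clock that is kept, every entry is zero.

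**The case against.** The best defence is that this is a disclosed exception with little effect. The exception stands directly below the rule and again in Table 1, so no site would be in doubt about what to do. The objectives concern the change over two hours of loading and do not name the 20-minute reading. Table 1 counts the recovery time from loading, and Table 3 counts it in the prone position, so an off-loading clock is the natural reading. The study is exploratory, has no primary outcome and is analysed mainly descriptively.

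Most of this stands, and it limits the point to the recovery reading and to a modest grade. It does not remove it. The 20-minute reading is a scheduled time point for seven outcomes, and section 3.2 gives it a purpose. Even with an off-loading clock, foam visits have less slack before the recovery round.

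A reader might infer three stronger things that the documents do not support:

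- *That the whole foam comparison is biased.* The two-hour heel and sacral readings precede the post-load OCT, and the plan gives no reason to think that some extra prone time before a fixed two-hour loading matters much.
- *That foam recovery is misstated by 11 to 50%.* Those percentages need an assumed OCT duration, an assumed half-life, exponential decay and the less natural clock, and they are fractions of what remains at the reading, not of the loading response.
- *That OCT disturbs the skin.* Nothing in the documents says so.

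Nor is foam named as the reference: the control that the plan names is sternal skin.

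**Conclusion.** The contradiction between the rule and the OCT restriction is explicit. OCT is fully aliased with foam, so the two foam contrasts at the 20-minute reading carry a procedural difference that neither the randomised order nor a model can remove. That much rests on the text alone.

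The confounding is structural; a bias is not demonstrated. Its size is unknown. It would be nil if the clock runs from off-loading, the post-load round with OCT finishes in time, and OCT leaves the skin unchanged. If the clock runs from the end of the round, a decaying response would look smaller on foam, so foam would appear to recover better. The point merits a change because the change is cheap before data collection and the difference cannot be undone by analysis afterwards.

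**What to change.** 1. On IsoAir and IsoGel visits, insert a pause at step 8 of the baseline and post-load rounds, in the same position and of the same fixed length as the time allotted to OCT on foam.
2. State in section 3.2, and in the same terms in Tables 1 and 3, that the 20 minutes start at off-loading on every visit. Confirm that the post-load round with OCT or pause fits into that interval.
3. Record the actual start and end time of each series.
4. State the OCT exception in the section 3.2 rule and in the Table 3 footnote.

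The cost is protocol wording and a few minutes on each non-foam visit. The pause equalises time and position; it would not equalise a direct effect of OCT on the skin, should one exist.

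Moving the post-load OCT to after the 20-minute round is not a good alternative. It would turn the two-hour OCT outcome into a recovery measurement: under the half-lives assumed above, 1 − 0.630 = 37% to 1 − 0.250 = 75% of a decaying response would be gone by 20 minutes. It would also leave the baseline OCT unmatched.

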3.3 Outcomes and variables

Because this is an exploratory study, no distinction will be made between primary and secondary outcomes.

Table 1. Outcomes

Name	Method and metric	Time points of data collection
TEWL	
 · Tewameter TM 300 (Courage + Khazaka, Cologne, Germany) · Means of duplicate measurements per skin area in g/m²/h 	BL, after 2 hours and 20 minutes after loading
Erythema	
 · Mexameter MX 18 · Means of duplicate measurements per skin area in arbitrary units 	BL, after 2 hours and 20 minutes after loading
SCH	
 · Corneometer CM 825 (Courage + Khazaka, Cologne, Germany) · Means of duplicate measurements per skin area in arbitrary units 	BL, after 2 hours and 20 minutes after loading
Skin roughness	
 · Visioscan VC 98 · Images of skin structure · Rz and Ra in µm 	BL, after 2 hours and 20 minutes after loading
Skin elasticity/deformability	
 · Cutometer MPA 580 (Courage& Khazaka, Germany) · Means of duplicate measurements per skin area in mm 	BL, after 2 hours and 20 minutes after loading
Skin surface temperature	
 · Measurement with Skin-Thermometer ST 500 · (Courage+Khazaka electronic GmbH) · Means of duplicate measurements per skin area in °C per skin area 	BL, after 2 hours and 20 minutes after loading
Epidermal and dermal hydration	
 · Measurement with MoistureMeterEpiD (Delfin Technologies) · Percentage of tissue water (0-100%) (0,5mm measurement depth) 	BL, after 2 hours and 20 minutes after loading
Epidermal/dermal characteristics (only for basic foam)	
 · OCT (Thorlabs, Lübeck, Germany), image processing and measurements according Trojahn et al. 2015 · Descriptive 	BL and after 2 hours
Skin thickness (only for basic foam)	
 · OCT (Thorlabs, Lübeck, Germany), image processing and measurements according Trojahn et al. 2015 · µm (metric) 	BL and after 2 hours

Table 2. Variables

Name	Method and metric	Time points
Age	Checking by looking at the ID card (metric)	Inclusion
Body temperature	Clinical thermometer in °C	BL, after two hours
Heart rate	Beats per minute (bpm)	BL, after two hours
Blood pressure	Millimeters of mercury (mmHg)	BL, after two hours
BMI (body height, weight)	kg/m ²	Inclusion
Phototype	Categories I, II, III	Inclusion

3.4 Participant timeline

Table 3. Participant timeline

	Inclusion	V1, V2, V3*				
		0 to 30 min (acclimatization)	Baseline measurements	2 hours (supine position)	Prone position	Prone position after 20 minutes
In-/exclusion criteria	x					
Signed Informed consent	x					
Demographics	x					
BMI	x					
Physical examination	x					
Marking of measurement areas	x					
Randomization	x					
Heart rate	x					
Blood pressure	x					
Body temperature	x					
Skin measurements at sternal skin			x	x		
Skin measurements at right heel and sacral skin			x		x	x
Adverse events monitoring		x	x	x	x	x

*same protocol on V1, V2, V3 (only change of support surface depending on randomized order), V3: end of study

3.5 Sample size

Due to the explorative nature of this study, a formal sample size estimation is not performed. However, considering the data of the previous study on a standard hospital mattress (Kottner et al. 2015) with $n = 15$, it is for instance possible, to detect a true difference in mean TEWL changes of approx. -8 or 8 $\text{g/m}^2/\text{h}$ with a probability of (power) 0.8 (alpha-level = 0.05) with an assumed standard deviation of 10 $\text{g/m}^2/\text{h}$. Observed TEWL changes at the heel skin were actually higher. Therefore we assume that the chosen sample size is sufficient to detect differences in support surface performance if they exist.

3.6 Recruitment

Potentially relevant subjects will be invited directly to participate by using the subject data base of the Clinical Research Center for Hair and Skin Science. The volunteers will be contacted by telephone.

4 Methods: assignment of interventions

